4.5 Exploratory Endpoint(s) Analysis

The exploratory endpoints are ophthalmic findings. All the assessments will be mapped to a scheduled visit. The mapping rule is provided in Table 2 for BCVA, OE and IOP and Table 3 for LLVA.

Best Corrected Visual Acuity (BCVA)

The score and the change from baseline of BCVA (ETDRS letters) at each analysis visit will be summarized descriptively by cohort for the FAS.

Low Luminance Visual Acuity (LLVA)

The score and the change from baseline of LLVA (ETDRS letters) at each analysis visit will be summarized descriptively by cohort for the FAS.

Low Luminance Deficits (LLD)

The score and the change from baseline of LLD (ETDRS letters) at each analysis visit will be summarized descriptively by cohort for the FAS, where LLD is calculated by the difference of BCVA and LLVA at a same visit.

Intraocular Pressure (IOP)

Baseline IOP is the pre-injection IOP value before the first study drug administration in this study.

Pre-injection IOP is defined as the last IOP value before an injection on a visit with injection (whether ACP or other treatment) or the last IOP value on a visit without an injection.

Post-injection IOP is defined as the IOP value after one injection that is closest in time to the protocol-specified post-injection timepoint (but at least 30 minutes post-injection).

Pre-injection and post-injection IOPs at each analysis visit will be summarized descriptively by cohort for the SAF with in one table. The number and percentage of participants in categories of pre-injection IOP value (≤ 21 mmHg, 22-29 mmHg, 30-34 mmHg, ≥ 35 mmHg) will be summarized at each analysis visit for each cohort.

The change from baseline of pre-injection IOPs will be summarized at each analysis visit for each cohort.

Change of IOP at each analysis visit is the difference between the post-injection and pre-injection IOPs. Change of IOP at each analysis visit will also be summarized descriptively for each cohort. The number and percentage of participants in categories of change of IOP (≤ 0 mmHg, 1-5 mmHg, 6-10 mmHg, >10 mmHg) will be summarized at each analysis visit for each cohort.

The number and percentage of participants who experienced the following events will be summarized for each cohort. The events are:

- Either pre-injection or post-injection IOP ≥ 35 mmHg,
- Had a paracentesis and
- Received IOP-lowering medications.

The number and percentage of injections with the following events will be summarized for each cohort. The events are:

- Either pre-injection or post-injection IOP ≥ 35 mmHg,
- Had a paracentesis.

Mean of pre-injection IOPs change from baseline and post-injection IOPs change from pre-injection will be plotted over time separately.

Ophthalmic Examination (OE)

The following OE variables will be analyzed for the SAF by a shift table (Normal/Abnormal/Missing) from Baseline to Month 18/End of Study (Early Withdrawal):

- Motility,
- Lids/Lacrimal/Lashes,
- Conjunctiva/Sclera,
- Cornea,
- Iris,
- Pupils,

- Posterior Vitreous Detachment,
- Optic Nerve,
- Macula,
- Retinal Vessels.

Participants with a change in lens status (aphakic, pseudo-phakic, phakic; if phakic, nuclear/PSC/cortical 0, 1, 2, 3, 4) will be listed for SE and FE.

Geographic Atrophy Area

Change from baseline in Geographic Atrophy Area of SE will be summarized descriptively at each analysis visit for each cohort.

4.6 Safety Analyses

All safety analyses will be performed on the SAF. Missing values of safety data will not be imputed, and safety summaries will be based on observed cases. ACP treated FE will not be considered as a second SE.

4.6.1 Adverse Events

All AEs will be coded in MedDRA. AE analysis will be based on the SAF.

A treatment-emergent adverse event (TEAE) is defined as an AE starting after the first administration of the study drug in this study until 30 days after the last administration of the study drug or until the last follow-up visit required by the protocol, whichever comes later.

An overview table to report the number and percentage of participants and number of events will include but not limited to the following:

- TEAEs,
- Drug related TEAEs,
- Serious TEAEs,
- Serious drug related TEAEs,
- TEAEs leading to withdrawal of study drug,
- Drug-related TEAEs leading to withdrawal of study drug,
- Severe TEAEs,
- TEAEs leading to death,
- Drug related TEAEs leading to death,
- Deaths.

An additional overview of TEAEs will be provided which displays the overall summary of TEAEs by three categories (SE, FE, and non-ocular).

The number and percentage of participants with TEAEs, as classified by SOC and PT will be summarized for each cohort. Summaries will be provided for the following:

- TEAEs,
- TEAEs with frequency of $\geq 5\%$ in any cohort,
- TEAEs with frequency of $\geq 2\%$ in any cohort,
- Non-serious TEAEs with frequency of $\geq 5\%$ in any cohort,
- Study drug related TEAEs,

- Injection procedure related TEAEs,
- Serious TEAEs,
- Serious study drug related TEAEs,
- Serious injection procedure related TEAEs,
- TEAEs leading to withdrawal of study drug,
- Study drug related TEAEs leading to withdrawal of study drug,
- Injection procedure related TEAEs leading to withdrawal of study drug,
- TEAEs leading to death,
- Study drug related TEAEs leading to death,
- Injection procedure related TEAEs leading to death.

Ocular TEAEs have been defined as TEAEs linked to the “Eye Disorders” SOC or the “Intraocular Pressure Increased” PT.

The number and percentage of participants with ocular TEAEs or non-ocular TEAEs, as classified by SOC and PT, will be summarized for each cohort. Summaries will be provided for those including but not limited to the following:

- Ocular TEAEs by SE and FE,
- Ocular TEAEs with frequency of $\geq 2\%$ in any cohort (by PT),
- Non-ocular TEAEs with frequency of $\geq 2\%$ in any cohort (by PT),
- Study drug related Ocular TEAEs (SE),
- Injection procedure related Ocular TEAEs (SE),
- TEAEs with high level term of cataract conditions by SE and FE,
- Serious ocular TEAEs (SE),
- Serious study drug related ocular TEAEs (SE),
- Serious injection procedure related ocular TEAEs (SE),
- Serious non-ocular TEAEs,
- Serious Study drug related non-ocular TEAEs,
- Serious injection procedure related non-ocular TEAEs,
- Ocular TEAEs (SE) leading to withdrawal of study drug,
- Non-ocular TEAEs leading to withdrawal of study drug,
- Study drug related non-ocular TEAEs leading to withdrawal of study drug,
- Injection procedure related non-ocular TEAEs leading to withdrawal of study drug,
- Ocular TEAEs (FE) on and after the initiation of the ACP treatment on FE,
- Ocular TEAEs (FE) on and after the initiation of the Syfovre treatment on FE.

The number and percentage of participants with TEAEs, as classified by SOC and PT will be summarized by severity for each cohort. If a participant has multiple TEAEs with the same SOC or PT, but with differing severity, then the participant will be counted once with the worst severity grade. If severity is missing of the event, the participant will be counted under missing severity. Summaries will be provided for the following:

- TEAEs,
- Study drug related TEAEs,
- Injection procedure related TEAEs,

- Ocular TEAEs (SE),
- Study drug related ocular TEAEs (SE),
- Injection procedure related ocular TEAEs (SE).

All AEs, including non-TEAEs, serious AEs, AEs leading to withdrawal of study drug and AEs leading to death will be listed.

The listings will include the subject identifier, age, sex, verbatim term, SOC, PT, eye (N/A / OD / OS / OU), serious (yes/no), date of onset, relative study day of onset, onset timing, duration of the event (or continuing), severity (mild/moderate/severe), causality (relationship to study drug/injection procedure), action taken (study drug permanently discontinued: yes/no), treatment required (yes/no), and outcome (resolved/not resolved/fatal).

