12.3 Definition of AESIs

The selection of adverse events of special interest (AESIs) are based on medical review of avacincaptad pegol AEs throughout the development program and the post-marketing environment. These include identified risks for an IVT injection procedure and potential risks for avacincaptad pegol mechanism of action, considering the frequency, seriousness, and medical plausibility of events.

The AESIs will include the following:

- Endophthalmitis
- Ischemic optic neuropathy
- Intraocular inflammation; any case of uveitis, retinal vasculitis or retinal occlusive vasculitis
- IOP \geq 30 mmHg at 30 minutes post injection deemed clinically significant by the Investigator
- Transient loss of light perception immediately after injection
- Elevation of IOP post-injection requiring surgical/procedural intervention (i.e., paracentesis; for instruction regarding paracentesis refer to [Appendix 17.2](#))
- BCVA decrease \geq 30 letters from ISEE2009 Month 1 Visit
- CNV (exudative or nonexudative)

AEs, as defined in [Section 12.1](#), should be reported as per [Section 12.2](#).

An AESI, as defined in this [Section 12.3](#), shall be reported if affecting the study eye. When an AESI occurs, the Investigator will fill out a standardized questionnaire to report the designated event in the same expedited manner as SAEs ([Section 12.5](#)).

Adverse events of CNV, endophthalmitis and intraocular inflammation occurring in the fellow eye, while not considered an AESI per protocol, shall be entered in the CRF as expeditiously as possible (i.e., within 24 hours of event).

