4.6.2 Adverse Events of Special Interest

The AESIs will include the following:

- Endophthalmitis,
- Ischemic optic neuropathy,
- Intraocular inflammation; any case of uveitis, retinal vasculitis, or retinal occlusive vasculitis,
- IOP \geq 30 mmHg at 30 minutes post injection deemed clinically significant by Investigator,
- Transient loss of light perception immediately after injection,
- Elevation of IOP post-injection requiring surgical/procedural intervention (i.e., paracentesis),
- BCVA decrease \geq 30 letters from ISEE2009 Month 1 Visit,
- Choroidal neovascularization (exudative or nonexudative),
- Macular oedema/cysts.

AESIs are TEAEs on SE. Both the AESI electronic case report form (eCRF) data and statistical programs will be used to identify AESI events. And the identification rules will be prespecified and documented in the TLF specifications.

The number and percentage of participants with AESIs within each AESI category will be summarized for each cohort. A listing will also be provided.

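### SAP 4.6.1 applies a coding filter before it looks at the recorded eye, so some events in a known eye can be tabulated as non-ocular

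*SAP*

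**What the plan says.** The primary endpoint is adverse events (Protocol 11.1; SAP 4.3), analysed in SAP 4.6. Section 4.6.1 sets the ocular rule: "Ocular TEAEs have been defined as TEAEs linked to the “Eye Disorders” SOC or the “Intraocular Pressure Increased” PT". On coding it says only: "All AEs will be coded in MedDRA. AE analysis will be based on the SAF". It gives no MedDRA version and does not say whether the link is to the primary SOC or to any SOC path.

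Non-ocular TEAEs have no definition of their own. By implication they are the remainder: "The number and percentage of participants with ocular TEAEs or non-ocular TEAEs, as classified by SOC and PT, will be summarized for each cohort". A separate overview "displays the overall summary of TEAEs by three categories (SE, FE, and non-ocular"), without saying whether it uses the coding rule or the recorded eye.

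The AE listings in the same section show the eye for each event, as not applicable, right, left or both. The definition does not refer to that field.

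For special-interest events, SAP 4.6.2 states "AESIs are TEAEs on SE". Protocol 12.3 asks for expeditious CRF entry of "Adverse events of CNV, endophthalmitis and intraocular inflammation occurring in the fellow eye", but says these are not AESIs. SAP 4.6 adds that a fellow eye treated with avacincaptad pegol (ACP) is not treated as a second study eye.

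**The concern.** For an intravitreal drug, the central safety question is harm to the injected eye. The ocular tables in SAP 4.6.1 are where a reader will look for it, by eye, relatedness, seriousness and severity. A rule based on one SOC plus one term lets dictionary placement, rather than the affected eye, decide what enters those tables.

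The SAP itself shows that the SOC alone is not enough. Naming raised IOP separately would be redundant if the SOC link already reached it, so at least one eye term sits outside. Only that one was added back.

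The excluded kinds of event are foreseeable in this trial. Protocol 12.1 brings clinically significant objective findings into AE reporting. Protocol 12.2 counts the speculum, drops, povidone-iodine, subconjunctival anesthetic and the injection itself as the injection procedure. Protocol Appendix 17.2 has patients taught the signs of endophthalmitis. If such events go to the non-ocular side, ocular summaries under-count and non-ocular summaries contain events that happened in an eye.

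**Working it through.** The plan gives no figure to reproduce: the trial is descriptive and the issue is a classification rule. The check is to apply the rule to each kind of eye event and then see where the event still appears.

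**Step 1. Two readings of *linked to*.** Reading A is primary SOC only, the usual basis for a table by SOC and PT. Reading B is any SOC path, primary or secondary. The SAP does not choose. Where each term sits in MedDRA is not in the documents, so the last two rows are conditional.

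| Event in an eye | Reading A | Reading B |
|---|---|---|
| Eye Disorders is the primary SOC | ocular | ocular |
| PT is Intraocular Pressure Increased | ocular (named) | ocular (named) |
| Other test-type eye finding, coded outside Eye Disorders with no path to it | non-ocular | non-ocular |
| Eye infection or procedural eye injury with another primary SOC | non-ocular | ocular if it has a secondary path |

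The third row fails under both readings and the fourth only under A. Two programmers could build different ocular tables from the same sentence.

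**Step 2. Where a study-eye event coded outside the filter appears.**
- Present: the tables of all TEAEs and, where they apply, the serious, drug-related and procedure-related tables; the matching severity tables for all, drug-related and procedure-related TEAEs; the listings, with the eye shown. If it meets an AESI category, as endophthalmitis does, it is also in the AESI table, which is built from the AESI eCRF and programs.
- Absent: the study-eye ocular TEAE table, the study-eye ocular tables by relatedness, seriousness and withdrawal, and the ocular severity tables.
- The named procedure-related non-ocular tables cover serious events ("Serious injection procedure related non-ocular TEAEs") and events leading to withdrawal. A non-serious procedure-related eye injury that did not lead to withdrawal would be in neither the study-eye procedure-related ocular table nor a named non-ocular counterpart, although the SAP's list is open-ended.

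**Step 3. Where a fellow-eye infection appears under Reading A.** It is not an AESI. It is outside the fellow-eye ocular table and outside the two tables of fellow-eye ocular TEAEs after the start of ACP or Syfovre in that eye. It remains in the all-TEAE tables, which do not separate by eye, and in the listings.

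**Step 4. The overview.** If it uses the recorded eye, its study-eye and fellow-eye counts will disagree with the ocular tables whenever such an event occurs. If it uses the coding rule, it labels an event in a known eye as non-ocular.

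**Step 5. Size.** The only input is the planned 280 participants. One misplaced participant is 1/280 = 0.36% of Total if all are treated. A single PT reaches the 2% tables in the Total column at 0.02 × 280 = 5.6, that is 6 participants. Cohort sizes are not stated; a smaller cohort reaches 2% with fewer. The documents give no rates for eye infections, procedural eye injuries or test-type eye findings coded outside the filter, so no expected count can be derived.

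**The case against.** The strongest reply is that this is a display rule in a study with no inference, and that nothing goes missing. Every event stays in the all-TEAE tables and in listings that show the eye, and the procedure-related and severity tables are also produced without an ocular restriction. Study-eye endophthalmitis has its own AESI row by cohort, found independently of the ocular rule. All of that stands.

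It is also fair that the eye is not wholly ignored: a table of ocular TEAEs by study and fellow eye cannot be made without it. The weakness is the order, since the coding filter comes first.

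A reader might infer that endophthalmitis and eye injuries certainly land in the non-ocular tables. The documents do not support that. It needs the primary-SOC reading and MedDRA placements that are not given. Naming the IOP term does not settle the reading: the sponsor may have added a term it knew had no path to the SOC.

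A reader might also infer that fellow-eye endophthalmitis would go unreported. It would not: Protocol 12.3 requires entry within 24 hours, and the listings show it. What could be missing is its count in the summaries by eye.

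What the reply does not answer is that, under either reading, an event in a known eye can be labelled non-ocular, and that the SAP does not say which reading applies.

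**Conclusion.** The point holds with moderate severity. It should be settled before database lock, but it does not threaten the primary endpoint as a whole.

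On the documents alone, the definition is a coding filter, the recorded eye comes second, the meaning of the link is unstated, and the overview's basis is unstated. That the filter can exclude test-type eye findings other than raised IOP rests on such terms having no path to Eye Disorders, which the separate naming of the IOP term makes plausible. That it can exclude eye infections and procedural eye injuries rests further on the primary-SOC reading.

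The consequence is under-counting in the study-eye ocular, procedure-related ocular and ocular severity tables. The least protected case is a fellow-eye infection, which has no AESI row and could be absent from the tables meant to show harm after ACP or Syfovre treatment of that eye. Numbers are likely to be small in percentage terms (0.36% of Total per participant), but the events concerned can be serious.

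**What to change.** In SAP 4.6.1, define an ocular TEAE as any TEAE with the eye recorded as right, left or both, mapped to study eye and fellow eye, and a non-ocular TEAE as one with the eye recorded as not applicable. Use the same flag in the study-eye, fellow-eye and non-ocular overview. Keep SOC and PT for display only.

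Before lock, query two kinds of record: Eye Disorders or IOP terms with the eye marked not applicable, and clearly non-ocular terms marked with an eye.

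If the coding rule is kept instead, state whether the link is to the primary SOC or to any path, give the MedDRA version, and prespecify a PT list covering infections, injuries and procedural complications, and investigations of the eye.

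The cost is one sentence, one derivation and some extra queries; the eye is already a listing field. Comparison with parent-study tables becomes less direct if those used the SOC rule. A SOC-based table can be kept as a supplement for that purpose.

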4 STATISTICAL ANALYSES

4.1 General Considerations

Continuous data will be summarized descriptively including the number of participants (n), mean, standard deviation (SD), median, minimum, Q1, Q3 and maximum. Categorical data will be summarized descriptively by frequencies and percentages. Percentages by categories will be based on the number of participants with no missing data, i.e., the percentages for the non-missing categories will add up to 100%. Participants with missing data are generally not included unless otherwise specified. When needed, the category of 'Missing' is created and the number of participants with missing data is presented.

All data summarization and analyses will be performed using SAS® Version 9.4 or higher on Red Hat Enterprise Linux. Specifications for table, figures, and data listing formats can be found in the Tables Listings Figures (TLF) specifications.

Summaries will be presented for the following cohorts unless otherwise specified:

- ACP EM to ACP EM, including all participants who received ACP every month (EM) through the Month 24 visit in the parent study ISEE2008 and enrolled in this study,
- ACP EM/EOM to ACP EM, including all participants who received ACP EM through the Month 11 visit and then randomized to ACP at Month 12 and administered ACP every other month (EOM) at Months 13, 15, 17, 19, 21, 23 in the parent study ISEE2008 and enrolled in this study,
- ACP to ACP EM, including all participants who received ACP EM through the Month 11 visit and then ACP EM or EOM through the Month 24 visit in the parent study ISEE2008 and enrolled in this study, which is the combination of the above two cohorts,
- Sham to ACP EM, including all participants who received Sham through the Month 23 visit in the parent study ISEE2008 and enrolled in this study,
- Total, including all participants who enrolled in this study regardless of the study drug and frequency they previously received in the parent study ISEE2008.

Baseline values will be defined as the last available value prior to the first administration of study drug in this study ISEE2009, unless otherwise specified.

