4.2.4 Previous and Concomitant Medications

Previous medications are defined as any medications that participants started prior to the first administration of the study drug in this study, including the medications that started before and during the parent study ISEE2008.

Concomitant medications are defined as any medications that participants took after the first administration of the study drug in this study and through the last follow-up visit in this study. Medications that started prior to and continued after first administration of study drug in this study will be counted in both previous and concomitant medications.

Previous and concomitant medications will be summarized separately by therapeutic subgroup (anatomical therapeutic chemical (ATC) 2nd level), chemical subgroup (ATC 4th level), preferred world health organization (WHO) name (active ingredients for combination drugs) and cohort for the FAS. Participants taking the same medication multiple times will be counted once per medication. A medication which can be classified into several chemical and/or therapeutic subgroups is presented in all chemical and therapeutic subgroups.

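### SAP 4.6.1: the two tables of fellow-eye events after fellow-eye ACP or Syfovre inherit a whole-cohort denominator, so their percentages are diluted by uptake

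*SAP*

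**What the plan says.** Among the ocular summaries in SAP 4.6.1 are two that concern treatment of the fellow eye (FE): "Ocular TEAEs (FE) on and after the initiation of the ACP treatment on FE" and "Ocular TEAEs (FE) on and after the initiation of the Syfovre treatment on FE".

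The sentence that introduces the list sets the statistic: "The number and percentage of participants with ocular TEAEs or non-ocular TEAEs, as classified by SOC and PT, will be summarized for each cohort". It adds: "Summaries will be provided for those including but not limited to the following".

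The population is set once for all adverse event tables: "AE analysis will be based on the SAF". SAP 4.6 says the same for safety analyses generally. SAP 3.2 defines the SAF as everyone given at least one dose of study drug.

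SAP 4.1 defines the cohorts by parent-study regimen. The last column is "Total, including all participants who enrolled in this study regardless of the study drug and frequency they previously received in the parent study ISEE2008".

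On FE treatment, SAP 4.6 says only that an ACP-treated FE is not analysed as a second study eye. Section 3 defines no set of FE-treated participants, and SAP 4.7 plans no subgroups.

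**The concern.** The two bullets restrict which events count: FE ocular events from the start of FE treatment with a named product. Nothing restricts who is counted underneath. A participant whose FE never received the product has no start date and cannot contribute an event, yet stays in the denominator.

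The percentage then mixes how often treated FEs have events with how many FEs were treated. A reader would naturally take it as the first. If uptake differs between cohorts, or between ACP and Syfovre, the printed percentages would differ even when the rates among treated FEs are the same. These are the only tables in SAP 4.6.1 restricted to FE events after FE treatment with either product.

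**Working it through.** **Step 1: which denominator the text gives.** There is no stated figure to reproduce, so this is a reading of the rules together.

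| Rule | Source | Limits the denominator to treated FEs? |
|---|---|---|
| Safety and adverse event analyses use the SAF | SAP 4.6, 4.6.1 | No |
| SAF is all participants with at least one dose of study drug | SAP 3.2 | No |
| Columns are parent-study cohorts and Total | SAP 4.1 | No |
| Percentages exclude participants with missing data | SAP 4.1 | No: an untreated FE is not a missing value |
| The two FE bullets | SAP 4.6.1 | No: they limit events only |

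The denominator is therefore the SAF count of each cohort.

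**Step 2: the effect.** Let N be the SAF participants in a column, m those whose FE received the product, u = m/N the uptake, and r the proportion of the m with an event.

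- Printed percentage = (r × m)/N = r × u.
- Percentage among treated FEs = r.
- Dilution factor = N/m = 1/u.

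**Step 3: illustration.** N = 280 is the planned enrolment (SAP 4.9), assuming all are dosed. Neither u nor r is in the documents; the values below are assumptions.

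| Assumed uptake | m | Dilution N/m | Printed % if r = 10% |
|---|---|---|---|
| 5% | 14 | 20 | 0.10 × 14/280 = 0.5% |
| 10% | 28 | 10 | 0.10 × 28/280 = 1.0% |
| 20% | 56 | 5 | 0.10 × 56/280 = 2.0% |
| 50% | 140 | 2 | 0.10 × 140/280 = 5.0% |

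With a treated-FE denominator, every row prints 10%.

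**Step 4: comparability.** Suppose two columns share r = 10% but have 5% and 20% uptake. They print 0.10 × 0.05 = 0.5% and 0.10 × 0.20 = 2.0%, a 4-fold difference due to uptake alone. The unequal uptake is hypothetical.

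**Step 5: follow-up, a secondary point.** On the SAP Table 2 schedule, Month 18 is Day 517. FE treatment started on Day 30 leaves 517 − 30 = 487 days; started on Day 487 it leaves 30 days. At a constant hazard giving 10% over 487 days, the 30-day risk is 1 − 0.9^(30/487) = 0.65%. A correct denominator does not remove this variation.

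**The case against.** **The TLF specifications may already set the right denominator.** They are not among the documents, and a column n is an ordinary table-shell item. The SAP also sends some substantive rules there, for special-interest event identification (4.6.2) and for additional analysis flags (4.10.1). But those delegations concern other topics. The general reference in SAP 4.1 covers formats only: "Specifications for table, figures, and data listing formats can be found in the Tables Listings Figures (TLF) specifications". What stands is that the denominator is inferred from general rules and is not stated for these tables in so many words.

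**A whole-cohort percentage is a legitimate measure of burden.** It is, for a table of all FE events. These tables start at treatment with a named product, so they inform mainly about those treated.

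**The number treated may be recoverable.** This largely stands. A reader might infer that no planned output bears on it, but the documents do not support that. SAP 4.2.4 states: "Previous and concomitant medications will be summarized separately by therapeutic subgroup". It goes down to WHO name and cohort, counting each participant once per medication. Study-eye ACP is study drug, so if FE ACP is coded as a concomitant medication, an ACP row would approximate the FE-treated count; a Syfovre row would give at least an upper bound. SAP 4.2 also plans a medication listing. The documents do not show how FE ACP is coded, and the two tables do not divide by the count in any case.

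**The magnitudes have no basis in the documents.** Correct. Only the relation r × u follows from the text.

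**Treated-FE columns would be small.** Also correct; the fix gives their likely size.

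**Conclusion.** The concern holds, as a minor point. Followed as written, SAP 4.6.1 prints percentages equal to the rate among treated FEs multiplied by uptake. They cannot be compared across cohorts or products if uptake differs. The direction is certain whenever uptake is below 100%. The size is not known: 2-fold to 20-fold for assumed uptake of 50% down to 5%.

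Two stronger readings are tempting and unsupported. One is that the trial's safety results are distorted: event counts in these tables are right, no hypotheses are tested (SAP 2), and the study-eye, special-interest and overall tables do not use this restriction. The other is that a misleading comparison of ACP with Syfovre, or between cohorts, is planned: the SAP describes none, and the risk lies in how a reader uses the columns.

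The conclusion assumes that the TLF specifications do not already override the general rule.

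**What to change.** Add to SAP 4.6.1, for these two tables only:

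*The denominator is the SAF participants who received the product concerned in the FE up to the end of the TEAE period, by cohort and in total; this n is printed. Initiation is the first FE administration of that product recorded in the CRF. An FE given both products appears in both tables and is footnoted.*

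Optionally, summarize follow-up after initiation (n, median, minimum, maximum), counted from the later of the first study dose and the first FE administration to the end of the TEAE period. All other tables stay as they are.

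The cost is a few lines in the SAP and TLF specifications and one derived date per product. Protocol 9.2.1 already requires FE treatments to be recorded in the CRF, so no new data are needed.

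The downside is small denominators. If 280 participants split like the treated parent arms (Protocol 4.4, 225 and 222 of 447), the columns hold 280 × 225/447 = 140.9 and 280 × 222/447 = 139.1. At 5%, 10% or 20% uptake that is about 7, 14 or 28 treated FEs per parent arm, and fewer once the ACP arm is divided by dosing frequency. The percentages need cautious reading, which the printed n makes plain.
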